## **1. PURPOSE, BACKGROUND, AND OBJECTIVES**

### **1.1 Purpose**

Atopic dermatitis (AD) is a common, chronic skin disease affecting 20% of children and 10% of adults worldwide (1-3). Children with AD often develop the disease within the first five years of life, which is a critical time for physical and psychosocial development (4). AD impacts an individual's physical, mental, and social health. Anxiety, itch, sleep disturbance, and depression have been associated with low quality of life scores. Childhood AD also affects the emotional, financial, physical, and social well-being of parents or caregivers (4). Individuals caring for a child with AD report sleep deprivation, poor social support, and stress about parenting (1, 4). Utilizing patient-reported outcomes (PROs) in clinic can provide meaningful data to monitor disease activity and response to different interventions, with the ultimate goal to improve quality of life for the patient and their family members or caregivers. Additionally, PROs can help us better understand the burden of AD. It is still unclear which PROs are most relevant for atopic dermatitis. This study will evaluate the utility of several PROs to monitor response to two different topical ointments, crisaborole (Eucrisa™) and tacrolimus 0.03%, to better understand the impact of these two non-steroidal topical treatments on overall health of children with AD of moderate or less severity and their caregivers.

### **1.2. Background**

AD can have detrimental impacts on overall quality of life for both patients and their families. PROs provide an efficient way to monitor the impact of disease and effect of treatment(s) on patients' physical, mental, and social health. Additionally, PROs can elucidate the impact of the disease on caregivers and families. Topical corticosteroids have been recommended as the first line treatment for AD, but their chronic use is associated with adverse effects, including dyspigmentation, telangiectasias, acne, and skin atrophy (5). Crisaborole (Eucrisa™) is a recently approved nonsteroidal topical ointment for the treatment of patients ( $\geq 2$  yrs of age) with mild to moderate AD. Crisaborole has a novel mechanism of action by inhibiting the phosphodiesterase-4 enzyme which has been shown to be elevated in AD leukocytes and is thought to be responsible for the tissue inflammation observed in this disease. Like tacrolimus, which has a different mechanism of action (e.g. calcineurin antagonist), it provides a safer alternative to topical steroids, which is especially relevant for children with AD. Unfortunately, it can be difficult to obtain prior authorization for this new medication. In contrast, tacrolimus 0.03% ointment is now available as a generic and is therefore much easier to prescribe because more insurance companies cover it for children (2-15yrs of age) with moderate AD. Many clinicians believe crisaborole to be more effective than tacrolimus; however long-term comparator studies have not been done. Paller *et al* showed that crisaborole was better than vehicle in children and adults with AD; however no baseline secondary measures (e.g., pruritus, signs of AD) were reported (5, 6). Nevertheless, recent post-hoc analysis of Phase 3 crisaborole studies observed a very early reduction in itch that may have a significant effect on patient and caregiver PROs (7) providing a potential advantage for crisaborole. This study will use a series of PROs to monitor the treatment effects of crisaborole and tacrolimus 0.03% over a 12 week period of time. The treatment for a chronic inflammatory disease characterized by flares and remissions must be longer than 30 days (i.e., 1 month) (5). We anticipate that crisaborole will

significantly decrease various PROs and that this effect will be superior to what is seen with tacrolimus 0.03%. We anticipate that the reductions we observe in the PROs will correlate with objective measures of disease severity (e.g. EASI).

### 1.3 Preliminary Studies

Our preliminary studies suggest the relevance of three PROMIS® domains (Pain Interference, Anxiety, Depression) to AD and treatment responses. In 101 adult AD patients, mean PROMIS® Depression and PROMIS® Anxiety scores were significantly higher for AD patients than all other dermatology patients (Depression =  $49.9 \pm 10.4$  vs.  $47.6 \pm 9.8$ ,  $p=0.030$ ; Anxiety =  $52.1 \pm 9.8$  vs.  $49.8 \pm 10.4$ ,  $p=0.017$ ). The percentage of AD patients with clinically significant (i.e., notable) scores (i.e.,  $>55$ ) was 36% in Anxiety, 33% in Mood, and 34% in Pain Interference. “Notable” Pain Interference scores associated with severe disease ( $p=0.020$ ), higher %BSA of disease ( $p=0.002$ ), uncontrolled disease ( $p=0.004$ ), and/or unsuccessful treatment ( $p=0.001$ ). Furthermore, Pain Interference decreased by a clinically important amount,  $7.0 \pm 11$  points, in patients who initiated systemic medication (e.g. dupilumab, cyclosporine, methotrexate, and/or mycophenolate mofetil) to treat their disease (53.9 to 46.9,  $p=0.029$ ). Depression also decreased by  $3.8 \pm 8.4$  points (51.6 to 47.8,  $p=0.050$ ). Further evaluation of the impact of other domains, such as itch and sleep, are necessary to fully understand how PROs can be used to monitor disease and treatment responses. Additionally, it is particularly important to understand the impact the disease (and treatments for the disease) have on caregivers. This study will elucidate the impact crisaborole has on children and caregiver PROs compared to tacrolimus 0.03%.

### 1.4 Objectives

**Primary Objective:** To investigate the effect of crisaborole (Eucrisa™) treatment on patient-reported itch and pain in patients with mild to moderate atopic dermatitis compared to tacrolimus 0.03%.

- *Hypothesis:* We hypothesize that crisaborole (Eucrisa™) treatment will significantly decrease (i.e., score change  $\geq 5$ ) the severity of itch and pain over time and these changes will correlate with improvements Eczema Area and Severity Index (EASI) in atopic dermatitis. We further hypothesize that the improvement in these PROs will be greater in the crisaborole treated subjects compared to those receiving tacrolimus.
- *Primary Outcome Measures:* Change in PROMIS® Itch and PROMIS® Pain Interference measures after 12 weeks of treatment.

**Secondary Objective:** To investigate the effect of crisaborole (Eucrisa™) treatment on patient-reported quality of life, sleep, anxiety, and depression in patients with mild to moderate atopic dermatitis compared to tacrolimus 0.03%.

- *Hypothesis:* We hypothesize that crisaborole (Eucrisa™) treatment will improve quality of life and decrease (i.e., score change  $\geq 5$ ) the severity of one or more of the PROs (sleep, anxiety, or depression). These changes will correlate with improvements in atopic dermatitis (EASI). We also hypothesize that the improvement in these PROs will be greater in the crisaborole treated subjects compared to those receiving tacrolimus.
- *Secondary Outcome Measures:* Change in Children’s Dermatology Life Quality Index (CDLQI), PROMIS® Anxiety, PROMIS® Depression, and Children’s Sleep Habits Questionnaire (CSHQ) after 12 weeks of treatment.

**Tertiary Objective:** To elucidate the impact of crisaborole (Eucrisa™) treatment or tacrolimus 0.03% on caregiver burden.

- *Hypothesis:* We hypothesize that improvements in caregiver burden will correlate with improvements in atopic dermatitis (EASI), as well as decreased severity in PROs.
- *Tertiary Outcome Measures:* Change in Caregiver Burden Inventory and Family Dermatology Life Quality Index (FDLQI) after 12 weeks of treatment.

## 2. STUDY DESIGN

### 2.1. Overview

This is an open-label, randomized, cross-sectional study to monitor the effects of crisaborole and tacrolimus 0.03% on patient-reported outcomes and caregiver burden in children (ages 2 to 15 years, inclusive) with ≤ moderate atopic dermatitis over a 12 week period of time. The goal of this study is to detect changes in PROs and caregiver burden during treatment for atopic dermatitis of moderate or less severity. The study design will allow us to correlate PROs and caregiver burden with treatment response and disease improvement in children.

Additionally, we will be able to determine if crisaborole is a better overall treatment for children with atopic dermatitis compared to tacrolimus 0.03%.

## 3. CHARACTERISTICS OF RESEARCH POPULATION

### 3.1. Number of Subjects

This study will enroll 40 patient and caregiver pairs (i.e., 20 patients and caregivers per topical treatment; 80 subjects total). Adjusting for potential 20% withdrawal or dropout rate, we will accrue up to 48 patient and caregiver pairs. Patients must be between the ages of 2 to 15 years with mild to moderate atopic dermatitis. Caregivers must be the adult parent or guardian (18 years or older) of the eligible patient. Further discussion of sample size and power of sample can be found §11.1 on page 23.

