- Study personnel will add appropriate subject information and study progress to the **Comprehensive Study Log**, as required by RSRB. This log is a password-protected excel file located in the study folder on the Dermatology CTU’s University sharedrive. Study personnel will only have access to this study folder and excel file.
- Subjects will be on study for at least 12 weeks. Subjects will be assessed at three different time points (Baseline, 6 Weeks, and 12 Weeks). Each assessment will be performed in the dermatology clinic and take approximately 30 minutes or less
- Pediatric subjects will be randomized 1:1 to one of two topical treatments: crisaborole or tacrolimus 0.03%. Both of these topical treatments are standard care for mild to moderate atopic dermatitis. Study personnel will obtain randomization in REDCap. After randomization, the treating dermatologist (i.e., [REDACTED]) will prescribe crisaborole or tacrolimus 0.03% to the pediatric subject for treatment of atopic dermatitis. Study personnel will dispense a tube of tacrolimus 0.03% or crisaborole to the subject based on randomization. The topical treatments will be applied to all affected areas twice daily for at least 12 weeks on this study. Additional tubes of tacrolimus 0.03% or crisaborole will be dispensed to the subject if needed to complete the 12 week treatment and assessment period. At the completion of the study, the treating dermatologist may continue or change the prescribed treatment for atopic dermatitis.
- Study personnel will complete the **ASPIRE On-Study Form** in REDCap. This form collects demographic information on both the pediatric subject and caregiver subject. Additionally, the form collects treatment information related to atopic dermatitis, all current medications, and medical history for the pediatric subject. This form will be completed after assent and consent are obtained.

- **Baseline Assessment:**
  - *Study personnel:* Trained study personnel (MD/NP) will perform Eczema Area & Severity Index (EASI), Investigator Static Global Assessment (ISGA), and Percentage Body Surface Area (%BSA) for the severity of atopic dermatitis. Study personnel will also weigh the tube of crisaborole and tacrolimus 0.03% prior to distribution to the subject. Study personnel will have an average weight for tube of tacrolimus prescribed. Study personnel will enter EASI, ISGA, and tube weight into the electronic **Assessment Form (Baseline)** in REDCap.

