## **7. SUBJECT WITHDRAWALS**

Subjects will be advised during the consent/assent process that they have the right to withdraw from the study at any time without prejudice or reason. Criteria for investigator-initiated subject withdrawal include: inability to make study visits, subject lost to follow-up, non-compliance to study procedures, or death. The reason for discontinuation will be recorded in the subject's medical records. The date of occurrence and reasons for any subject withdrawal will be recorded and documented on the **Withdrawal Form**. Subjects that withdraw from the study will be replaced with another subject.

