### **11. DATA ANALYSES AND MONITORING**

#### **11.1. Sample Size Determination**

We will accrue 48 patient and caregiver pairs, accounting for 20% withdrawal or dropout rate, to ensure evaluation of 40 patient and caregiver pairs (i.e., 20 per AD patient/caregiver pairs per topical treatment). All statistical tests will be performed at the two-tailed 0.05 level of significance. For an effect size of 5.0 in a population with standard deviation of 10.0, a sample size of 16 will provide 80% power to detect a score change of 4 in the two primary outcome measures. An electronic medical record search for the last year counted 900 patients with the diagnosis of atopic dermatitis between the ages of 1 and 17 years. However, it is unclear how many of these patients have mild or moderate AD. We will enroll a total of 40 evaluable patients and caregivers (i.e., 20 per AD treatment; 80 total participants). Our sample size will allow us to detect a change of at least 4 (i.e., clinically significant change) in the itch and pain PROs between baseline and 12 weeks of treatment. Subjects that complete at least the 6 week assessment will be considered evaluable. In this study, the superiority of crisaborole is not dependent on the clinical change (EASI); superiority is dependent on significant changes in PROs and their potential correlation with EASI. Therefore, crisaborole would be superior to tacrolimus if crisaborole improves PROs (and/or caregiver burden), but its clinical effectiveness (EASI) is not statistically significantly different than tacrolimus.

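### Accrual of 48 pairs is 40 × 1.2, not 40 / 0.8 = 50: at a 20% loss between accrual and evaluability, 48 pairs are expected to leave about 38 evaluable, so they do not ensure 40

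*Combined protocol and SAP*

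**What the plan says.** Section 3.1 (Number of Subjects) plans 40 pairs, 20 per topical treatment, and then adds: "Adjusting for potential 20% withdrawal or dropout rate, we will accrue up to 48 patient and caregiver pairs".

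Section 11.1 (Sample Size Determination) repeats this with a stronger promise: "We will accrue 48 patient and caregiver pairs, accounting for 20% withdrawal or dropout rate, to ensure evaluation of 40 patient and caregiver pairs". Both enrolment tables in section 3.8 also total 48.

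Three other statements bear on the figure:

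- Section 11.1 defines evaluability by the middle visit: "Subjects that complete at least the 6 week assessment will be considered evaluable".
- Section 7 (Subject Withdrawals) has a replacement rule: "Subjects that withdraw from the study will be replaced with another subject". It does not say whether replacements count within the 48.
- Section 1.4 (Objectives) sets the primary outcomes as change in PROMIS Itch and PROMIS Pain Interference after 12 weeks, and section 11.2 runs the primary analysis from baseline to 12 weeks.

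The documents do not say whether the 20% is loss to week 6 or to week 12, or how the losses divide between those periods.

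**The concern.** A dropout rate is a fraction of the subjects who enter. To keep a target number after losing a fraction *d*, the target is divided by (1 − *d*). Multiplying by (1 + *d*) always gives too few, and 48 is what multiplying gives here. Section 11.1 uses the 20% as the allowance between accrued and evaluable pairs, and on that use 48 does not reach 40 on average.

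What is at stake is modest. A stated sample size and the assurance attached to it do not agree with the plan's own loss rate. The text also does not let a reader tell when accrual stops: section 3.1 gives a maximum, while section 7 promises replacement without a limit.

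**Working it through.** **Inputs**

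- Target: 40 evaluable pairs, 20 per arm (sections 3.1 and 11.1).
- Loss rate: 20% (sections 3.1 and 11.1).
- Accrual: 48 pairs (sections 3.1 and 11.1).
- Allocation: 1:1 (section 5.1).

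**1. Reproducing the plan's figure.** Target × (1 + *d*) = 40 × 1.20 = 48. This matches exactly.

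**2. The standard inflation.** Target / (1 − *d*) = 40 / 0.80 = 50 pairs, 25 per arm. The plan is 2 pairs lower.

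**3. What 48 pairs leave at 20% loss.** 48 × 0.80 = 38.4 pairs, or 24 × 0.80 = 19.2 per arm. The expected shortfall is 40 − 38.4 = 1.6 pairs.

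**4. The loss that 48 pairs can absorb.** 1 − 40/48 = 16.7%.

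**5. The chance of at least 40 evaluable out of 48.** This assumes independent losses, X ~ Binomial(48, 1 − loss), and accrual ending at 48.

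| Loss before evaluability | Expected evaluable | P(X ≥ 40) |
|---|---|---|
| 10% | 43.2 | 0.95 |
| 15% | 40.8 | 0.71 |
| 16.7% | 40.0 | 0.59 |
| 20% | 38.4 | 0.36 |

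With 50 pairs and 20% loss the chance is 0.58, so even correct inflation gives 40 on average and does not guarantee it.

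**6. Replacement inside the 48.** Suppose 40 pairs start and up to 8 replacements follow. If the replacements are lost at the same rate, the expected number when all 48 places are used is 40 × 0.8 + 8 × 0.8 = 38.4. Reaching 40 still requires 40 evaluable among at most 48 accrued, so the probability is again 0.36. Replacing until 40 are evaluable, with no ceiling, takes 40 / 0.8 = 50 pairs on average.

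**7. The week 6 definition.** Let *f* be the share of the 20% lost before week 6. The documents do not give *f*, so this is an assumed range. Expected evaluable = 48 × (1 − 0.20*f*).

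| *f* | Expected evaluable |
|---|---|
| 50% | 43.2 |
| 75% | 40.8 |
| 83% | 40.0 |
| 100% | 38.4 |

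The break-even is *f* = 16.7% / 20% = 83%.

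**8. Week 12.** If the 20% is the total loss by week 12, then 48 × 0.80 = 38.4 pairs remain at the primary time point, whatever *f* is.

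**9. Consequence for the between-arm comparison.** For a difference of 5 and SD of 10 (the section 11.1 figures), two-sided 0.05, the two-sample t-test has power of about 34% at 20 per arm and about 32% at 19 per arm.

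**The case against.** The strongest reply is that the 20% is labelled a withdrawal or dropout rate, not a rate of loss before week 6. A pair that leaves between weeks 6 and 12 is a dropout but still evaluable under section 11.1. On that reading 48 pairs are expected to yield 40 or more evaluable unless more than about 83% of the losses come early. Section 7 also replaces withdrawals. If replacements may go beyond 48, the target of 40 can simply be filled. The wording in section 3.1, which makes 48 a maximum, can even be read as 40 plus as many as 8 replacements, so that inflation and replacement are one mechanism. And the gap is 2 pairs at most.

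Much of this stands. A reader might infer that the evaluable size of 40 will definitely not be delivered. The documents do not support that: the shortfall needs both a ceiling of 48 that includes replacements and a loss falling almost wholly before week 6. A reader might also infer that the power statement rests on an overstated number per arm. It does not. That sentence in section 11.1 uses a sample size of 16, which is below both 19 and 20, and it has a separate error of its own.

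The reply does not rescue the stated arithmetic. Section 11.1 itself uses the 20% to get from accrued to evaluable pairs, and on that use the result is 38.4. Replacement inside the 48 does not change it (step 6). If replacements may exceed 48, then the maximum in section 3.1 is not a maximum, and sections 3.1 and 7 need reconciling. The week 6 definition protects the count of evaluable pairs, but it does not supply week 12 data, which the primary outcomes require.

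**Conclusion.** The point holds as a minor arithmetic and wording error. Sections 3.1 and 11.1 multiply where they should divide. With 20% lost between accrual and evaluability, independent losses, and accrual capped at 48 including replacements, about 38 evaluable pairs (19 per arm) are expected, and the chance of reaching 40 is about 36%. The assurance in section 11.1 is therefore not supported.

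The expected shortfall in evaluable pairs disappears if no more than about 83% of the losses precede week 6, or if replacements may exceed 48. At week 12, a total loss of 20% from 48 pairs leaves about 38. That is an upper figure for the primary measures, because section 5.1 has children under 5 complete no self-report measures.

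The effect on power is too small to change any conclusion.

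**What to change.** In sections 3.1 and 11.1:

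1. Restate the figure in one of two ways: 48 pairs tolerate a loss of up to 16.7% on average while leaving 40, or 48 pairs at 20% loss give about 38 evaluable (19 per arm).
2. Remove the word *ensure* from section 11.1.
3. Say whether the 20% is loss to week 6 or to week 12.
4. Reconcile the maximum of 48 in section 3.1 with the replacement rule in section 7 by saying whether replacements count within the 48.

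The power sentence should not be edited to read 19 per arm on account of this point. It is built on a sample size of 16 and needs its own correction.

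The cost is wording only, with a slightly less favourable stated size. No additional pairs are required if the plan keeps 48 and states what it delivers.

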### 3.2. Gender of Subjects

There are no restrictions based on gender in this study. A recent study involving parent participation reported 84% of participating caregivers were female (8).

### 3.3. Age of Subjects

This study enrolls children between the ages of 2 to 15 years with mild to moderate atopic dermatitis. This study also enrolls caregivers, who must be the adult (18 years or older) parent or guardian of the eligible patient.

### 3.4. Racial and Ethnic Origin

There are no restrictions based on race or ethnicity in this study. Based upon an ethnic minority population of 16% in the six county area of Rochester, we expect Rochester accruals to be at least 12% minority. Atopic dermatitis is prevalent in African Americans.

### 3.5. Inclusion Criteria:

#### Pediatric Subjects:

- a) Male and female subjects of inclusive ages of 2 to 15 years at screening visit.

- b) Diagnosis of  $\leq$ moderate atopic dermatitis or eczema (ISGA 2 or 3 and  $\geq 3\%$  BSA, excluding scalp).
- c) If subject is taking or prescribed antihistamines, subject must be on stable dose of antihistamines.
- d) If subject is taking topical steroids, subject must be on stable dose of topical steroid.
- e) Subjects currently taking tacrolimus (i.e., Protopic), crisaborole (i.e., Eucrisa), or other topical steroid-sparring medications are eligible for this study if he/she agrees to a two week “washout period” prior to starting study procedures (See “washout period” described below on page 9).
- f) If subject is taking systemic anti-inflammatory therapy (i.e., cyclosporine, etc), subject must be on a stable dose of the systemic anti-inflammatory medication for at least six week prior to enrollment and it must be anticipated that this dose would not change during their participation in this study, unless deemed medically necessary. Any changes in medication dose due to flaring of atopic dermatitis or side effects will be documented on the *AD Flare Medication Form* and *AE Source Doc* (see page 19).
- g) Caregiver (i.e., adult parent or guardian) must agree to participate in the study with the patient.
- h) Subject must be able to read and speak English.
- i) Subject, ages  $\geq 8$  years, is able to give assent.

